3.4 Randomization and blinding

Patients will be prospectively randomized into the PILLAR III Clinical Trial. Randomization will occur at the time of surgery, just after induction of anesthesia. Prior to surgery the patient will have provided written informed consent, completed all baseline procedures and met the requirements of the study inclusion and exclusion criteria. Randomization should be performed as closely as possible to the point of resection to minimize the incidence of dropout.

Patients will be randomly assigned on a one to one (1:1) basis to either the PERFUSION group (PFN) or the STANDARD group (STD). Randomization will be stratified by study site and within site by the patients history of prior neoadjuvant therapy (chemotherapy and/or radiation vs. non-neoadjuvant therapy) to ensure a more even distribution of baseline neoadjuvant therapy between treatment groups. Permuted block randomization will be performed within strata. To minimize the opportunity for the sequence to be predicted, the block size will be variable and randomly chosen from small multiples of 2 (i.e. 2, 4 or 6). The randomization schedules for all strata will be generated in advance by the contracted study statistician or designee using a computerized random number generator. Investigational sites and the Study Sponsor will not have access to the randomization schedules.

Randomization will be accomplished using a sequential numbered sealed envelope system. Due to stratification for prior neoadjuvant therapy, a box of envelopes will be supplied for each strata (one for subjects who have received prior neoadjuvant therapy and another for subjects who have not received prior neoadjuvant therapy). Envelope seals are broken and treatment assignment is made only after verification of proper informed consent execution and study eligibility. In order to prevent any attempts to subvert the randomization process, the subject's initials, date of birth, and date of randomization will be written on the randomization card. The randomization card will be signed by the study coordinator performing the randomization procedure and a second researcher who will witness the randomization procedure.

In the event of the subjects not following the randomization plan, selection bias would occur. In this situation, a conservative approach would be taken, where safety analyses would be carried out using actual treatment while efficacy analyses carried out using planned treatment. Such subjects will be documented.

In the event of subjects opting out of randomization in favor of the investigational product, sampling bias would occur. These subjects would not be included in the analyses, thus, skewing the results such that they would not be representative of the true population. If sicker patients were to select the investigational product and not be included in the analysis, the results would represent a less sick population than that of the true population.

	Forms			
	Title	Statistical Analysis Plan Template		
	Code	Version	Effective Date	Page
	FRM_ST03_032	01	23 Apr 2015	13 of 20

3.5 Efficacy endpoints

3.5.1 Primary endpoint

Incidence of post-operative anastomotic leak in each study arm.

3.5.2 Secondary efficacy endpoints

- Proportion of PERFUSION arm subjects in whom the PINPOINT or SPY Elite system provided sufficient visualization for assessment of blood flow and related tissue perfusion during the procedure.
- Incidence of post-operative abscess in each study arm.

3.6 Safety endpoints

- Incidence of treatment related adverse device events and surgical complications.
- Clavien-Dindo grading of post-operative complications.
- Concomitant medications and procedures.

4. Statistical Analysis

4.1 General

Categorical variables will be summarized with the number and percent of subjects in each group. Continuous variables will be summarized with the mean, standard deviation, median, minimum, and maximum values. 95% confidence intervals will be calculated for the primary and secondary endpoints.

All data collected in the CRF will be presented in the listings.

4.2 Analysis sets

4.2.1 Screened

Subjects considered potential candidates for the study based on pre-screening will sign an IRB/EC approved Informed Consent Form (ICF) prior to any study activities. The Investigator or delegated study research staff may then complete the first study visit with the subject.

4.2.2 Randomized

The randomized population includes all randomized subjects.

4.2.3 Modified Intent-to-Treat (mITT)

	Forms			
	Title	Statistical Analysis Plan Template		
	Code	Version	Effective Date	Page
	FRM_ST03_032	01	23 Apr 2015	14 of 20

The mITT analysis population includes all randomized subjects in whom a low anterior resection surgical procedure is initiated or at least one injection with ICG was performed. Subjects who have the surgical resection procedure aborted due to circumstances such as a higher stage cancer than initially anticipated will not be included in the mITT population. Subjects will be analyzed according to their randomized group assignment. The mITT population will be used for all efficacy analyses.

4.2.4 As-Treated (AT)

The As-Treated (AT) analysis population includes all randomized subjects in whom the intended open, or minimally invasive low anterior resection surgical procedure and, if assigned to the PERFUSION arm, PINPOINT or SPY Elite NIR fluorescence imaging with at least one perfusion assessment using ICG was successfully performed. Subjects in whom the intended surgical procedure is not performed or imaging with PINPOINT or SPY Elite was not successful are excluded from the AT population. mITT subjects not included in the AT population will be followed in the same manner as mITT subjects who do meet AT population inclusion criteria. Subjects will be analyzed according to the treatment actually received.

The AT population will be used for a secondary analysis of the primary endpoint.

4.2.5 Per-protocol (PP)

The Per-protocol (PP) population will consist of all AT subjects that: [1] meet critical study eligibility criteria; [2] have no significant protocol deviations; and [3] have evaluable assessment for the primary study endpoint.

The PP population will be used for subset analysis of the primary endpoint.

4.2.6 Safety

The safety analysis population includes all randomized subjects. Secondary safety endpoints including the summary of adverse events in the trial will be analyzed using this analysis population, divided into groups according to actual use or non-use of PINPOINT and SPY Elite.

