## 1.2 Previous Human Experience

Several studies using similar technology to PINPOINT and SPY Elite have been conducted to investigate the feasibility of using NIR ICG induced fluorescence angiography in assessing tissue perfusion during colorectal resection to potentially reduce the rate of anastomotic leak have been published.

The PILLAR II study was conducted to demonstrate the utility and feasibility of intra-operative perfusion assessment using PINPOINT NIR ICG induced fluorescence angiography at the time of anastomosis creation.

One hundred and forty-seven patients were enrolled, of whom 139 were eligible for final analysis. The average age of patients was 58  $\pm$ 14 years, and 53% of patients were male. Obesity (Body Mass Index [BMI]  $>30$ ) was prevalent in 30% and the majority of patients were American Society of Anesthesiologists (ASA) II (53%). Diverticulitis (44%), rectal cancer (25%) and colon cancer (21%) were the most prevalent pre-operative diagnoses. Of the patients with rectal cancer (N=35), 43% underwent pre-operative pelvic radiation. Cardiovascular disease (44%), and urogenital disease (40%) were the most prevalent comorbidities.

Laparoscopic resection was attempted in 86% and robotic surgery in 14% of the patients imaged. There was an overall conversion rate of 7.8% (N=12), of which 5 patients were imaged, and 7 patients were dropped out of analysis due to intraoperative decision to not image. The splenic flexure was mobilized in 81% of patients, and a high ligation of the inferior mesenteric artery (IMA) was performed in 62% of cases. Successful imaging was obtained in 98.6% of cases in which perfusion imaging was attempted. Imaging was unsuccessful in 2 patients secondary to equipment malfunction. Fluorescence angiography imaging changed the surgical plan in 11 (7.9%) patients. This included revision of the point of proximal colon transection as indicated by perfusion assessment in 9 patients (6.5%); takedown and revision of anastomosis after transanal perfusion assessment in one patient; and confirmation of viability of anastomosis where there was concern based on white light imaging in one patient. The use of fluorescence angiography with findings of adequate perfusion altered the intraoperative plan for diversion to no diversion in this patient. There were no anastomotic leaks in the 11 patients in whom a change in the surgical plan occurred based on fluorescence angiography findings.

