## **5 RANDOMIZATION, BLINDING AND SUBJECT IDENTIFICATION PROCEDURES**

### **5.1 Randomization**

Patients will be prospectively randomized into the PILLAR III Clinical Trial. Randomization will occur at the time of surgery, just after induction of anesthesia. Prior to surgery the patient will have provided written informed consent, completed all baseline procedures and met the requirements of the study inclusion and exclusion criteria. Randomization should be performed as closely as possible to the point of resection to minimize the incidence of dropout.

Patients will be randomly assigned on a one to one (1:1) basis to either the PERFUSION group (PFN) or the STANDARD group (STD). Randomization will be stratified by study site and within site by the patients history of prior neoadjuvant therapy (chemotherapy and/or radiation vs. non-neoadjuvant therapy) to ensure a more even distribution of baseline neoadjuvant therapy between treatment groups. Permuted block randomization will be performed within strata. To minimize the opportunity for the sequence to be predicted, the block size will be variable and randomly chosen from small multiples of 2 (i.e. 2, 4 or 6). The randomization schedules for all strata will be generated in advance by the contracted study statistician or designee using a computerized

random number generator. Investigational sites and the Study Sponsor will not have access to the randomization schedules.

Randomization will be accomplished using a sequential numbered sealed envelope system. Due to stratification for prior neoadjuvant therapy, a box of envelopes will be supplied for each strata (one for subjects who have received prior neoadjuvant therapy and another for subjects who have not received prior neoadjuvant therapy). Envelope seals are broken and treatment assignment is made only after verification of proper informed consent execution and study eligibility. In order to prevent any attempts to subvert the randomization process, the subject's initials, date of birth and date of randomization will be written on the randomization card. The randomization card will be signed by the study coordinator performing the randomization procedure and a second researcher who will witness the randomization procedure.

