## 9.4 Surgical Complications: Special Instructions

Anastomotic leaks, and strictures or abscesses that require intervention should be reported and followed as SAEs for this study.

Subjects who present with a clinical suspicion of anastomotic leak during the study will have a computerized tomography (CT) scan to confirm unless the patient’s condition warrants urgent operative intervention. A leak is considered confirmed if endoluminal contents (air, gastrointestinal contents or contrast material) through the anastomosis occur. The presence of infection or abscess thought to be related to the anastomosis may be classified as an anastomotic leak at the surgeon’s discretion even if it cannot be definitively identified as visualized during an operation or by contrast extravasation. An abscess adjacent to the anastomosis containing air will be classified as a leak. All Anastomotic leaks will be followed until resolution.

Specific post-operative complications are defined as follows for this study and should be reported as surgical complications and SAEs if they meet SAE criteria at the time of the event:

- Prolonged post-operative NPO or nasogastric tube (NGT) use is defined as prolonged NPO status or NGT use for more than 3 post-operative days (POD4 or later), or the return to NPO status or insertion(or presence) of NGT anytime POD4 or later within 30 days.
- Post-operative ileus is defined as insertion or reinsertion of a NGT after surgery or a return to NPO status for nausea and/or vomiting with failure of passage of flatus and/or stool.
- A small bowel obstruction is defined as radiologic or operative evidence of an obstruction.

All adverse events and post-operative complications occurring during the study period will be graded according to the following Clavien-Dindo classification system^20 as shown in Table 2. Grades will be recorded on the CRF.

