To evaluate the effectiveness of assessing perfusion of colon and rectal tissue using PINPOINT or SPY Elite in reducing the incidence of post-operative abscess requiring surgical management:

Letting p_t and p_c respectively represent the treatment-group and control-group incidence of post-operative abscess requiring surgical management, the following hypotheses will be tested:

$$H_0: p_t = p_c$$

$$H_1: p_t < p_c$$

The statistical test will be a z-test using pooled variance estimate and no continuity correction. In the case of small counts, an exact procedure will be used. Descriptive statistics and 95% confidence intervals will be calculated for p_t , p_c , and $(p_t - p_c)$.

Then secondary efficacy endpoints will be analyzed on the mITT population.

7. Evaluation of Safety

The number of AEs, ADEs, SAEs, UADEs, and the number and the percentage of patients experiencing AEs, SAEs, ADEs, UADEs will be presented for the safety set.

AEs will be coded using the MedDRA dictionary (version 18.0). The SOCs and PTs will be used for tabulation.

The number of AEs and the number and the percentage of patients with at least one AE will be presented by SOC and PT for AEs, SAEs.

	Forms			
	Title	Statistical Analysis Plan Template		
	Code	Version	Effective Date	Page
	FRM_ST03_032	01	23 Apr 2015	19 of 20

All adverse events and post-operative complications occurring during the study period will be graded according to the Clavien-Dindo classification system.

The number and the percentage of patients with at least one AE and ADE will be presented by SOC, PT and Clavien-Dindo classification system.

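### Safety results are tabulated only by actual device use, so PERFUSION subjects who are never imaged are counted with the STANDARD subjects, which may bias the complication comparison

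*SAP*

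**What the plan says.** SAP 4.2.6 and Protocol 10.6 define the safety set as all randomized subjects, "divided into groups according to actual use or non-use of PINPOINT and SPY Elite". SAP 3.4 gives the same rule for departures from the randomization plan: "safety analyses would be carried out using actual treatment while efficacy analyses carried out using planned treatment". It calls this conservative and says such subjects will be documented. SAP section 7 states that the counts and percentages of AEs, ADEs, SAEs and UADEs "will be presented for the safety set", and adds tables by Clavien-Dindo grade. No safety table by randomized arm is named.

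The safety endpoints in SAP 3.6 go beyond device effects: "Incidence of treatment related adverse device events and surgical complications", together with Clavien-Dindo grading of post-operative complications.

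Efficacy is handled differently. SAP 4.2.3 reads: "Subjects will be analyzed according to their randomized group assignment. The mITT population will be used for all efficacy analyses". Leak (primary) and abscess requiring surgical management (secondary) are therefore compared by randomized arm. Protocol 9.4 also makes these events safety data: "Anastomotic leaks, and strictures or abscesses that require intervention should be reported and followed as SAEs for this study".

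**The concern.** Grouping by actual use is right for reactions to ICG and for hardware effects, which need exposure. Surgical complications and their grades are outcomes of the whole operation, and for those the grouping variable should not depend on how the operation went. Here it can. Protocol 5.1 says: "Randomization will occur at the time of surgery, just after induction of anesthesia". Under Protocol 8.3.2.2 the first imaging comes only after mobilization, distal transection and ligation of the IMA and IMV. Whatever goes wrong in between can decide whether imaging takes place.

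Protocol 1.2 shows this happening in PILLAR II. Of 12 converted patients, 5 were imaged and "7 patients were dropped out of analysis due to intraoperative decision to not image".

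A never-imaged PERFUSION subject is not dropped but moved to the comparator column. If such subjects have more complications than the rest, one move lowers the use column and raises the non-use column. Two things are at stake. Equal arms could look different, and a real excess of complications in the PERFUSION arm could be hidden. In addition, one leak can count in the PERFUSION arm for efficacy and in the non-use column as an SAE.

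**Working it through.** **The plan's own figures.** The plan states no safety rate, so there is none to reproduce. Its design power does reproduce. Pocock-type spending at the interim look is 0.025 × ln(1 + (e − 1) × 450/800) = 0.0169. The bounds are z = 2.122 and 2.220, and pooled-variance power at 12.5% against 6.25% is 81.6%. That figure concerns leak by randomized arm and is not affected here.

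**Inputs from the documents**
- 1:1 allocation (Protocol 5.1) and a planned 800 subjects (Protocol 10.4), so n = 400 per arm. SAP 3.3 instead takes whoever is enrolled through March 31, 2017. The bias in points does not depend on n (see the general form).
- Never imaged in PILLAR II: 7/147 = 4.8%. The conversion figure printed beside it (12 patients, 7.8%) implies about 12/0.078 = 154 patients, which would give 7/154 = 4.5%. The difference does not matter here.

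**Assumed inputs.** The documents give no complication rates. Rate if imaged: a = 20%. Rate if never imaged: h = 30%, 40% or 50%. Never-imaged PERFUSION subjects: m = 12, 20 or 32 (3%, 5% or 8% of 400). No STANDARD subject is imaged, and the arms are truly equal.

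**Formulas**
- True rate in each arm: p = [a(n − m) + hm]/n
- Use column: a
- Non-use column: (np + mh)/(n + m)

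| m | h | True rate, both arms | Use column | Non-use column | Apparent difference |
|---|---|---|---|---|---|
| 12 | 30% | (77.6 + 3.6)/400 = 20.3% | 20.0% | (81.2 + 3.6)/412 = 20.6% | 0.6 points |
| 20 | 40% | (76 + 8)/400 = 21.0% | 20.0% | (84 + 8)/420 = 21.9% | 1.9 points |
| 32 | 50% | (73.6 + 16)/400 = 22.4% | 20.0% | (89.6 + 16)/432 = 24.4% | 4.4 points |

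**General form.** Let R be the common arm rate, f the share of the PERFUSION arm never imaged, and kR the rate in that share. The use column is (R − fkR)/(1 − f) and the non-use column is (R + fkR)/(1 + f). Their difference (use minus non-use) is 2fR(1 − k)/(1 − f²). The sign depends only on k. With f = 7/147 and R = 30% (assumed):
- k = 2: 28.5% against 31.4%, or −2.9 points.
- k = 1.5: 29.3% against 30.7%, or −1.4 points.
- k = 1: no difference.
- k = 0.5: 30.8% against 29.3%, or +1.4 points, so the bias runs against the device.

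**A hidden excess.** Suppose the true rates are 33% (PERFUSION) and 30% (STANDARD), with f = 7/147 and k = 2. The use column is (0.33 − 0.0314)/0.9524 = 31.4% and the non-use column is (0.30 + 0.0314)/1.0476 = 31.6%. A true excess of 3 points appears as −0.3 points. By randomized arm it appears as +3.0.

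**The case against.** The actual-use grouping is deliberate: SAP 3.4 states it and promises to document the subjects concerned, and SAP 4.1 lists all CRF data. It is the right grouping for device effects. The safety tables are descriptive, with no hypothesis test attached. The complications that imaging is meant to prevent are compared by randomized arm in the mITT set. The central case of 1.9 points is below one standard error of the difference: √[0.21 × 0.79 × (1/380 + 1/420)] = 2.9 points. The 4.8% comes from a study of laparoscopic and robotic cases with a different case mix. In this trial SPY Elite may be used in open procedures, so conversion need not prevent imaging. All of this stands and limits the weight of the point. It does not supply the missing by-arm table.

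Four stronger readings are tempting and are not supported:
- *Any subject whose imaging is abandoned moves to the controls.* Use is not defined. On a plain reading, a subject who is injected or imaged before imaging is abandoned stays in the use group. Only never-imaged subjects clearly move.
- *The grouping flatters the device.* That requires k above 1. PERFUSION cases aborted before imaging have no anastomosis, stay in the safety set and may pull the other way. Imaged STANDARD subjects would enter the use column, and complications among them would count there.
- *A disagreement between the SAE table and the primary result could come only from the grouping.* The mITT set leaves out aborted resections, the leak estimate leaves out leak-free subjects with under 6 weeks of follow-up (SAP 6.1), and the independent radiologist's reading is final for suspected-leak scans (Protocol 13.4).
- *By-arm tables must replace the actual-use tables.* Which display should lead is debatable. Having both is not.

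**Conclusion.** The point holds as a possible bias in a descriptive comparison. For AEs, SAEs, surgical complications and Clavien-Dindo grades, the only grouping named is actual use, which is decided after randomization, and a never-imaged PERFUSION subject is counted with the STANDARD subjects. Under the assumed rates, equal arms would appear to differ by about 0.6 to 4.4 points. The direction depends on the never-imaged subjects having more complications than the rest, which is plausible from the PILLAR II conversions but not established for this trial. Only the 7 of 147 comes from the documents; every complication rate is an assumption. The randomized comparisons of leak and of abscess requiring surgical management are untouched, although the same events reported as SAEs are regrouped by use.

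**What to change.** In SAP 4.2.6 and section 7, and in Protocol 10.6:
- Add tables of AEs, SAEs, surgical complications and Clavien-Dindo grades by randomized arm, beside the actual-use tables.
- Keep actual use for ADEs, UADEs and ICG reactions.
- Define use, for example as any ICG injection or any device imaging.
- List subjects whose use differs from their assignment, with the reason. This extends the documentation already promised in SAP 3.4.

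The cost is a change of wording and one extra set of tables from data already collected.

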4.3 Pooling of sites

The homogeneity of effectiveness results across study sites will be examined and if no significant heterogeneity is found, the results will be pooled. A logistic regression will be employed modeling the proportion of subjects with post-operative anastomotic leak with treatment, center, and treatment by center interaction as fixed effects. If treatment by center interaction is not significant when compare to an alpha of .05, it can be determined that there is no heterogeneity of treatment effect across centers. It is not anticipated that any individual study site will dominate the study results. Therefore, it is believed that the data from these study sites can be combined and analyzed as if generated at a single site.

